9.5.4 Pharmacodynamic and Biomarkers Analysis

The PD and biomarkers are explorative for this study. These data will be listed only.

Descriptive statistics will be the primary methods for the exploratory analyses. Among the variables to be included in the exploratory analyses are:

- Correlation analysis between PD biomarkers and the disease response to treatment with NC762.

The immunogenic potential of NC762 will be assessed by summarizing the number and percentage of subjects who develop detectable ADAs. The impact of ADAs on PK will be assessed if data allow. Samples will be collected for evaluating neutralizing capacity of ADAs in the future.

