A Phase 1/2, Open-Label, Dose-Escalation, Safety and Tolerability Study of NC762 in Subjects with Advanced or Metastatic Solid Tumors

Sponsor Protocol Number: NC762-01

IND Number: 145522

Investigational Product: NC762

Humanized immunoglobulin gamma 1, kappa (IgG₁κ) monoclonal antibody specific for human B7 homolog 4 (B7-H4) protein

Phase of Study: 1/2

Sponsor:
NextCure, Inc.
[name]
[name]

[REDACTED]
[REDACTED]

Medical Monitor:

[REDACTED]
[REDACTED]
[REDACTED]
[REDACTED]

Original Protocol (Version 1.0)	12Feb2021
Amendment 1 (Version 2.0)	09Apr2021
Amendment 2 (Version 3.0)	07Jul2021

Protocol Synopsis

TITLE 
A Phase 1/Phase 2, Open-Label, Dose-Escalation, Safety and Tolerability Study of NC762 in Subjects with Advanced or Metastatic Solid Tumors

HYPOTHESES 
NC762 will be adequately tolerated following administration in multiple ascending doses to subjects with refractory solid tumors and that such administration may result in clinical benefit.

OBJECTIVES Primary Objectives 
1) To evaluate the safety, tolerability, and dose-limiting toxicities (DLTs) of NC7622) To define a maximum tolerated dose (MTD) or pharmacologically active dose (PAD) of NC762 Secondary Objectives 
1) To evaluate the pharmacokinetic (PK) profile of NC7622) To assess preliminary efficacy of NC7623) To evaluate downregulation of B7-H4 expression and changes in tumor infiltrating lymphocytes after NC762 treatment. Exploratory Objectives 
1) To assess the immunogenicity of NC7622) To explore biomarkers that may predict the pharmacologic activity of NC762
STUDY ENDPOINTS Primary Endpoints 
1) Safety and tolerability will be assessed by monitoring frequency, duration, and severity of adverse events (AEs). Note: Toxicity grading per NCI CTCAE v5.02) The MTD or PAD of NC762 will be defined in subjects with advanced or metastatic solid tumors Secondary Endpoints 
1) Assessment of PK of NC762 will include individual NC762 concentrations in serum and identification of PK parameters.2) Assessment of antitumor activity/efficacy will include objective response (OR) and disease control rate (DCR) based on RECIST v1.1, duration of response (DoR),

progression-free survival (PFS), and overall survival (OS) as per RECIST v1.1 and mRECIST v1.1

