- 3) Tumor biopsy analyses to evaluate downregulation of B7-H4 expression and changes in tumor infiltrating lymphocytes after NC762 treatment.

Exploratory Endpoints

- 1) Immunogenicity, defined as the occurrence of anti-drug antibodies (ADA) to NC762, will be determined.
- 2) Biomarker effects of NC762 in peripheral blood and tumor tissue will be assessed, including but not limited to the following:
 - Whole blood immune cell population profiling/immune-phenotyping.
 - Serum markers of inflammation or immune modulation (cytokine levels).
 - The expression of additional histological biomarkers may also be assessed.

STUDY DESIGN

This is an open-label, nonrandomized, Phase 1/2 study to determine the safety and tolerability, define the MTD or PAD, and to assess the preliminary efficacy of NC762 in subjects with advanced or metastatic solid tumors. Subjects will receive NC762 on Day 1 of each cycle. Phase 1 of the study will begin with 14-day cycles; however, alternate dose administration schedules may also be explored depending on PK, pharmacodynamic (PD), biomarker, safety results, and feedback from investigators. The study will be conducted in 2 parts:

- Phase 1 – Dose Escalation and Safety Expansion will determine the PAD, defined as a dose that provides a maximal biologic effect, such as an increase in biomarkers of immune activation or reduction of markers associated with immunosuppression, and/or the MTD of NC762, including defining the optimal dose administration schedule and the maximum number of tolerated doses (MNTD).
- Phase 2 – Dose Expansion will evaluate the recommended dose and administration schedule determined in Phase 1 in subjects with non-small cell lung (NSCLC) (squamous cell), hepatocellular carcinoma (HCC), HER2+ breast, and ovarian cancer. These proposed indications may change based on emerging data.

Phase 1a – Dose Escalation

In Phase 1a, subjects with advanced or metastatic solid tumors who progressed after treatment with therapies known to confer clinical benefit, are intolerant to treatment, or refuse standard treatment will be enrolled. A 3 + 3 design will be utilized to determine the MTD of NC762.

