2 OBJECTIVES AND ENDPOINTS

2.1 Objectives

2.1.1 Primary Objectives

- 1) To evaluate the safety, tolerability, and dose-limiting toxicities (DLTs) of NC762
- 2) To define an MTD or PAD of NC762

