2.1.2 Secondary Objectives

- 1) To evaluate the PK profile of NC762
- 2) To assess preliminary efficacy of NC762
- 3) To evaluate downregulation of B7-H4 expression and changes in tumor infiltrating lymphocytes after NC762 treatment.

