2.2.2 Secondary Endpoints

- 1) Assessment of PK of NC762 include individual NC762 concentrations in serum and identification of PK parameters.
- 2) Assessment of antitumor activity/efficacy include objective response (OR) and DCR based on RECIST v1.1, DoR, PFS, and overall survival (OS) as per RECIST v1.1 and mRECIST v1.1
- 3) Tumor biopsy analyses to evaluate downregulation of B7-H4 expression and changes in tumor infiltrating lymphocytes after NC762 treatment.

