3.1 Description of the Study

This is an open-label, nonrandomized, Phase 1/Phase 2 study to determine the safety and tolerability, define the MTD or PAD, and to assess the preliminary efficacy of NC762 in subjects

with advanced or metastatic solid tumors. Subjects will receive NC762 on Day 1 of each cycle. Phase 1 of the study will begin with 14-day cycles; however, alternate dose administration schedules may also be explored depending on PK, PD, biomarker, safety results, and feedback from investigators. The study will be conducted in 2 parts:

- Phase 1 – Dose Escalation (Phase 1a) and Safety Expansion (Phase 1b) will determine the MTD and/or the PAD, defined as a dose that provides a maximal biochemical effect, or an increase in biomarkers of immune activity. It will also define the optimal dose administration schedule and the maximum number of tolerated doses (MNTD).
- Phase 2 – Dose Expansion will evaluate the recommended dose and administration schedule determined in Phase 1 in subjects with advanced or metastatic non-small cell lung (squamous cell), hepatocellular carcinoma, HER2+ breast, and ovarian cancer, or other tumor type as identified with emerging data.

Figure 1: Study Design

RR: Response Rate (ORR) per RECIST v1.1

3.1.1 Phase 1

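### Section 9.5.4 labels all PD and biomarker data exploratory and listed only, so secondary endpoint 3 (tumor B7-H4 and TIL change) has no specified estimate; separately, the PAD has two differing definitions

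*Combined protocol and SAP*

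**What the plan says.** Section 2.1.2 gives the third secondary objective as "To evaluate downregulation of B7-H4 expression and changes in tumor infiltrating lymphocytes after NC762 treatment", and Section 2.2.2 gives the matching endpoint as "Tumor biopsy analyses to evaluate downregulation of B7-H4 expression and changes in tumor infiltrating lymphocytes after NC762 treatment". The exploratory endpoints have their own list in Section 2.2.3: immunogenicity, blood immunophenotyping, serum cytokines and additional histological biomarkers.

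The analysis text in Section 9.5.4 makes no such distinction: "The PD and biomarkers are explorative for this study. These data will be listed only". Its next sentence reads "Descriptive statistics will be the primary methods for the exploratory analyses", and the section then names one variable, the correlation of PD biomarkers with disease response, before turning to anti-drug antibodies.

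Section 7.8.1.1 makes a pre-screening biopsy and a Cycle 3 on-treatment biopsy mandatory in Phase 1b and Phase 2. Biopsies are optional in Phase 1a.

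Biomarker data also bear on the primary objective in Section 2.1.1, "To define an MTD or PAD of NC762". The synopsis describes the PAD as "defined as a dose that provides a maximal biologic effect, such as an increase in biomarkers of immune activation" and adds a fall in immunosuppression markers as a further example. Section 3.1 describes it as "defined as a dose that provides a maximal biochemical effect, or an increase in biomarkers of immune activity".

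**The concern.** A secondary endpoint should have a planned estimate. Here the only analysis section that could cover the tumor biopsy endpoint downgrades it to exploratory and limits it to a listing. A listing of individual values gives no average change, no measure of precision and no comparison across doses or tumor cohorts. Subjects in Phase 1b and Phase 2 must undergo an invasive on-treatment biopsy, and the plan does not say what quantity will be estimated from it. If the summary is chosen after the data are seen, the scale, the time point and the subjects counted all become open choices.

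The PAD wording is a second, separate problem. The same dose could meet one definition and not the other.

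**Working it through.** **1. Rank of the endpoint.** Sections 2.1.2 and 2.2.2 and the synopsis all place tumor B7-H4 and TIL change at the secondary level. Section 2.2.3 lists the exploratory items separately, and its histology item covers only additional markers. Section 9.5.4 applies one exploratory label to all PD and biomarker data with no exception. The rank in the endpoint sections and the rank in the analysis section cannot both hold.

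**2. Is the endpoint analysed elsewhere?**
- Section 9.5.1 covers safety.
- Section 9.5.2 covers PK.
- Section 9.5.3 covers ORR, DCR, DoR, PFS and OS, with 95% exact CIs for ORR and DCR.
- Section 9.5.4 mentions neither B7-H4 nor TILs.
- Section 9.1 defines a full analysis set, a safety set and a PK set, but no set of subjects with paired biopsies.

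No section gives the tumor biopsy endpoint a summary measure.

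**3. What a paired summary would deliver.** The documents give no figure to reproduce and no SD for the paired change, so the results are in units of that SD. For n evaluable pairs, the 95% CI half-width for the mean paired change is t(0.975, n−1)/√n.

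| Setting | n | Calculation | Half-width (SD) |
|---|---|---|---|
| One Phase 1b cohort (3.1.1.2) | 10 | 2.262/√10 | 0.72 |
| Phase 2 cohort stopped after Stage 1 (3.1.2) | 12 | 2.201/√12 | 0.64 |
| All Phase 1b pooled (3.1.1.2) | 20 | 2.093/√20 | 0.47 |
| Full Phase 2 cohort (9.2.2) | 24 | 2.069/√24 | 0.42 |

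Each row assumes that every subject supplies an evaluable pair. If only half of a full cohort of 24 did so, the half-width would be that of the n = 12 row, 0.64 SD. No row is given for Phase 1a, because optional biopsies make the number of pairs unpredictable.

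**4. The two PAD definitions side by side.**
- *A rise in an immune-activity marker that is not maximal.* Section 3.1 can accept it, because it joins the two conditions with an alternative. The synopsis does not, because there a rise only illustrates a maximal effect.
- *A maximal fall in immunosuppression markers.* The synopsis names it. Section 3.1 does not, so it would count there only if read as a biochemical effect.

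Neither definition names a marker, a time point or a threshold.

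**The case against.** The strongest defence is that 9.5.4 does not stop at listings. It goes on to descriptive statistics and a correlation with response. The opening of Section 9 sets a default for continuous variables (mean, SD, median and range, by dose group) and defers further detail to a SAP. Section 9.3 plans no hypothesis test, so nothing confirmatory depends on this endpoint.

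Part of this stands. A reader might infer that the biopsy data will certainly go unsummarised, or that the trial cannot answer its secondary question. The documents do not support that: the text contradicts itself and leaves the analysis unspecified, which is different from ruling out any summary. But the sentence on descriptive statistics covers only exploratory analyses. The Section 9 default specifies neither a paired change nor a CI, and the specific listing-only rule displaces it. The supplied document contains no further SAP text on the endpoint, and deferring detail would not settle a conflict of rank. The absence of testing does not remove the need for an estimate.

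A reader might also infer that the mandatory biopsies exist only for this endpoint. They do not: the pre-screening biopsy serves B7-H4 eligibility.

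On the PAD, a reader might infer that the Section 3.1 wording lets any chance increase name a dose, and that the synopsis wording guards against this. Neither follows. No section makes an observed increase select a dose automatically. Sections 3.1.1.2 and 9.2.1 leave the recommended dose to the sponsor and investigators on the totality of safety, PK, PD and biomarker data. With no drug effect, some dose would still show the largest observed effect, so the synopsis wording is no safer against noise.

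**Conclusion.** The point holds as a conflict between endpoint rank and analysis rule, with a gap as its result: the plan specifies no estimate for secondary endpoint 3. The text alone establishes this, and no numerical assumption is needed. It should be corrected, but it does not threaten the safety evaluation or the response-based decisions in Phase 2.

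The half-widths, from 0.72 SD for a Phase 1b cohort of 10 to 0.42 SD for a full Phase 2 cohort, show that the planned numbers support a useful if imprecise estimate. They assume complete, evaluable pairs and roughly normal paired changes on the chosen scale. Tumor data from Phase 1a may be too sparse for by-dose estimates.

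The PAD definitions do differ, and the difference can change how a dose is classified. The documents support no stronger claim than that the two passages must be reconciled.

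**What to change.** In Section 9.5.4, take secondary endpoint 3 out of the exploratory, listing-only sentence and give it its own paragraph:

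- **Measure:** paired change from the pre-treatment biopsy to the Cycle 3 biopsy, for example the log ratio of B7-H4 score and of TIL density.
- **Set:** subjects with an evaluable pair, defined alongside the other sets in Section 9.1.
- **Presentation:** by dose level and by Phase 2 cohort, with the number of evaluable pairs, the mean change or geometric mean ratio, and its 95% CI. Phase 1a results are shown where pairs exist.

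Keep the other biomarkers exploratory with descriptive summaries, and delete the listing-only wording so that the section no longer contradicts itself.

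Separately, the sponsor should reconcile the PAD definitions in the synopsis and Section 3.1. Which wording to keep is the sponsor's decision.

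The cost is a wording amendment and a few tables from samples already scheduled. No visits, biopsies or subjects are added.

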9.6 Analyses for Data Monitoring Committee

Not applicable.

10 STUDY AND DATA MANAGEMENT

10.1 Training of Study Site Personnel

Before the first subject is entered into the study, a NextCure representative will review and discuss the requirements of this protocol and related documents with the investigational staff and train them in any study-specific procedures and system(s) utilized.

The Principal Investigator (PI) will ensure that appropriate training relevant to the study is given to all of these staff, and that any new information relevant to the performance of this study is forwarded to the staff involved.

The PI will maintain a record of all individuals involved in the study (medical, nursing and other staff).

10.2 Monitoring of the Study

During the study, a NextCure representative will have regular contacts with the study site, including visits to:

- Provide information and support to the investigator(s).
- Confirm that facilities remain acceptable.
- Confirm that the investigational team is adhering to the protocol, that data are being accurately and timely recorded in the eCRFs, that biological samples are handled in

accordance with the NC762-01 Laboratory Manual and that study drug accountability checks are being performed.

- Perform source data verification (a comparison of the data in the eCRFs with the subject's medical records at the hospital or practice, and other records relevant to the study) including verification of informed consent of participating subjects. This will require direct access to all original records for each subject (e.g., clinic charts).
- Ensure withdrawal of informed consent to the use of the subject's biological samples is reported and biological samples are identified and disposed of/destroyed accordingly, and the action is documented, and reported to the subject.

The NextCure representative will be available between visits if the investigator(s) or other staff at the center needs information or advice about the study conduct.

10.2.1 Source Data

All source documents should be completed in a neat, legible manner to ensure accurate interpretation of data. Data reported in the eCRF derived from source documents should be consistent with the source documents.

The primary source document for this study will be the subject's medical record. If the investigator(s) maintains separate research records, both the medical record and the research records will be considered the source documents for the purposes of auditing the study.

Data recorded on source documents will be entered into eCRFs. The investigator must promptly review the completed eCRFs for each subject. A study monitor representing the sponsor will review the source documents against the eCRF on a regular basis throughout the study.

The PI at each/the center should comply with all the terms, conditions, and obligations of the Clinical Trial Agreement, or equivalent, for this study. In the event of any inconsistency between this protocol and the Clinical Trial Agreement, the terms of the protocol shall prevail with respect to the conduct of the study and the treatment of subjects and in all other respects, not relating to study conduct or treatment of subjects, the terms of the Clinical Trial Agreement shall prevail.

Agreements between NextCure and the PI must be in place before any study-related procedures can take place, or subjects are enrolled.

10.2.2 Archiving of Study Documents

The Investigator follows the principles outlined in the Clinical Trial Agreement and according to the ICH-GCP and applicable regulatory requirements. Records will be retained for at least 2 years after the last marketing application approval or 2 years after the study is discontinued and the FDA is notified.

10.3 Study Timetable and End of Study

An individual subject will be considered to have completed the study if the subject was followed through the last protocol-specified visit/assessment (including telephone contact), regardless of the number of doses of investigational product that was received.

Subjects will be considered not to have completed the study if consent was withdrawn or the subject was lost to follow-up (see [Section 5.5.1](#)).

The end of the study (“study completion”) is defined as the date of the last protocol-specified visit/assessment (including telephone contact) for the last subject in the study.

10.4 Data Management

Data management will be performed according to the study specific Data Management Plan.

A web based Electronic Data Capture (EDC) system will be used for data collection and query handling. The investigator will ensure that data are recorded on the eCRFs as specified in the study protocol and in accordance with the instructions provided.

The investigator ensures the accuracy, completeness, and timeliness of the data recorded and of the provision of answers to data queries according to the Clinical Trial Agreement. The investigator will sign the completed eCRFs. A copy of the completed eCRFs will be archived at the study site.

10.5 Medical Monitor Coverage

Each subject will be provided with contact information for the PI and the site coordinator(s). In an emergent situation, a subject may present to a medical facility where the treating health care provider is not involved with this clinical trial. The treating healthcare provider may require additional information on the study drug, and the subject should provide contact information for the site coordinator(s) or the PI.

The PI will then be required to update the medical monitor.

11 ETHICAL AND REGULATORY REQUIREMENTS

11.1 Ethical Conduct of the Study

The study will be performed in accordance with ethical principles that have their origin in the Declaration of Helsinki and are consistent with ICH/Good Clinical Practice (GCP), and applicable regulatory requirements.

11.2 Subject Data Protection

The ICF will incorporate (or, in some cases, be accompanied by a separate document incorporating) wording that complies with relevant data protection and privacy legislation.

The anonymity of subjects must be maintained. Subjects will be identified by their initials and an assigned subject number on eCRFs and other documents submitted to the sponsor. Documents that identify the subject beyond initials and subject number will not be submitted to the sponsor (e.g.; the signed ICF) and must be maintained in strict confidence by the investigator, except to the extent necessary to allow auditing by the regulatory authorities, site monitor, or sponsor representatives.

NextCure will not provide individual genotype results to subjects, any insurance company, any employer, their family members, general physician, or any other third party, unless required to do so by law.

Extra precautions are taken to preserve confidentiality and prevent genetic data being linked to the identity of the subject. In exceptional circumstances, however, certain individuals might see both the genetic data and the personal identifiers of a subject. For example, in the case of a medical emergency, a NextCure medical monitor or an investigator might know a subject's identity and also have access to his or her genetic data. Also, Regulatory authorities may require access to the relevant files, though the subject's medical information and the genetic files would remain physically separate.

11.3 Ethics and Regulatory Review

An IRB/IEC should approve the final study protocol, including the final version of the ICF and any other written information and/or materials to be provided to the subjects. The investigator will ensure the distribution of these documents to the applicable IRB/IEC, and to the study site staff.

The opinion of the IRB/IEC should be given in writing. The investigator should submit the written approval to the sponsor or designee before enrollment of any subject into the study.

The IRB/IEC should approve all advertising used to recruit subjects for the study.

The sponsor or designee should approve any modifications to the ICF that are needed to meet local requirements.

If required by local regulations, the protocol should be re-approved by the IRB/IEC annually.

Before enrollment of any subject into the study, the final study protocol, including the final version of the ICF, is approved by the national regulatory authority or a notification to the national regulatory authority is done, according to local regulations.

The sponsor or designee will handle the distribution of any of these documents to the national regulatory authorities.

The sponsor or designee will provide Regulatory Authorities, IRB/IEC, and PIs with safety updates/reports according to local requirements, including suspected unexpected serious adverse reactions (SUSARs), where relevant.

Each PI must inform the IRB/IEC of:

- Changes in informed consent
- Revisions of other documents originally submitted for review
- Serious and/or unexpected AEs occurring during the study
- New information that may adversely affect the safety of subjects or the conduct of the study
- Annual update and/or request for re-approval
- Study completion

